## 4.10 Efficacy Evaluation

### 4.10.1 Analysis and Data Conventions

This study is designed to evaluate the superiority of two doses of OTT166 (5 mg/day and 10 mg/day) compared to vehicle control for the treatment of DR. For each dose within each endpoint, the null hypothesis is that there is no difference between OTT166 and vehicle control or the difference is in the direction of inferiority of OTT166, and the alternative hypothesis is that there is a difference between OTT166 and vehicle control in the direction of superiority of OTT166.

All statistical tests will be one-sided and will be performed at the 5% level of significance, unless otherwise stated. The vehicle control group will be combined for all efficacy analyses and two-sided 90% confidence intervals will be presented. A comparison between the two control groups will be performed for the primary endpoint to confirm the groups are comparable.

#### 4.10.1.1 Adjustments for Covariates

The primary efficacy analysis will be adjusted for the randomization stratification factor, the Screening DRSS score (47 or 53 or 61B).

#### 4.10.1.2 Handling of Missing Data and Data After Intercurrent Events

##### Primary Efficacy Analysis:

Handling of missing DRSS response at Week 24 data in participants without ICEs:

- Multiple imputation assuming missing at random (MAR).

Handling of DRSS response at Week 24 data missing after ICEs:

- Single imputation (non-response) when applying composite variable strategy.
- Multiple imputation assuming MAR when applying hypothetical and treatment policy strategy.

Handling of DRSS data response at Week 24 observed after ICEs:

- Replaced by non-response (single imputation) in the analysis when applying composite variable strategy.
- Replaced by MAR multiple imputation algorithm based on data from participants not affected by the respective ICE when applying hypothetical strategy.
- Kept in the analysis when applying treatment policy strategy.

If a participant experiences more than one ICE, ICE(s) with a composite variable strategy take priority over ICEs with hypothetical strategies, which take priority over ICEs with a treatment policy strategy.

MAR imputation will be generated based on a regression model for DRSS levels with covariates for randomized treatment group and the randomization stratification variable. DRSS response will be derived based on the imputed values. A total of 100 imputations will be used, followed by the MIANALYZE procedure to combine the estimates.

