
Designation of Study Eye:
 
Only one eye will be designated as the study eye in every participant. For participants who meet eligibility criteria in both eyes during the screening phase, the eye with the higher reading center confirmed DRSS should be selected. If both eyes have the same score, the eye with the clearest lens and ocular media will be selected. If there is no objective basis for selecting the study eye, factors such as ocular dominance (better focus ability), other ocular pathology, and participant preference should be considered in making the selection. The final selection will be done by the Investigator in discussion with the participant at baseline and must not be changed during the course of the study.
 
The non-study eye is eligible for treatment according to the standard of care treatments through the duration of the study.
	

Study procedures/assessments:
 
Assessments will be performed monthly during each clinic visit unless indicated otherwise in the Schedule of Activities (SoA), and include the following:
 
 • Adverse event recording • Review of concomitant medications • Vital signs • Physical examination (Screening Visit only) • Laboratory testing (hematology, blood chemistry, urinalysis, and HbA1c) • Pregnancy testing (as applicable) • BCVA (ETDRS) • Slit-lamp bio-microscopy • Ocular surface health [fluorescein stain of the cornea] • IOP • Indirect ophthalmoscopy/dilated fundus examination • Spectral domain OCT (SD-OCT) (central subfield thickness, macular volume, foveal contour) at every visit 	

- 7-field or 4-wide field color fundus photography at every visit [optional wide-field if available]
- DRSS scoring, based on 7-field or 4-wide field photos by the PI at baseline to confirm eligibility
- Fluorescein angiography (FA) (wide field if available) at baseline and end of study
- OCTA if available (for exploratory endpoints) at baseline and end of study
- Rescue therapy initiation, per alignment between Investigator and Medical Monitor
- HbA1c at screening and end of treatment
- Gonioscopy

Visit Timeline:

Screening – Visit 1; Baseline (BL) – Visit 2; Week 4 – Visit 3; Week 8 – Visit 4; Week 12 – Visit 5; Week 16 – Visit 6; Week 20 – Visit 7; Week 24 – Visit 8

Rescue Criteria:

Participants meeting any of the following criteria would qualify for rescue with anti-VEGF therapy and/or PRP laser after consultation with the Medical Monitor:

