2.14.6 Stopping Rules (Study Level)

The following criteria result in an immediate stop of dosing and will result in a temporary halt of the study:

Any relevant information, from this trial or from outside of this trial, indicating a relevant deterioration of the benefit-risk ratio. In particular, consistently observed serious adverse events (SAEs) or severe drug-related AEs will be thoroughly assessed by the medical monitor and Study Steering Committee.

Resuming the trial after a temporary halt requires an approved substantial amendment. For discontinuation of study intervention for individual study participants, see [Section 2.14.10](#).

2.14.7 *Continued Access to Study Intervention After the End of the Study*

No treatment with study medication will be provided after the end of the planned 24-week treatment period or after early withdrawal of treatment.

2.14.8 *Concomitant and Prohibited Therapy in the Study Eye*

No other ocular topical drugs (eye drops) should be taken during the study unless prescribed by the treating study physician and after discussion with the sponsor and medical monitor. If topical therapy (eye drops) is prescribed, the application of such therapy should not occur within 10 minutes (before or after) of instillation of study therapy. Other approved or investigational therapies for retinal disease (ie, oral, topical, and/or intravitreal injected drugs like steroids or anti-VEGFs) are not permitted, unless applied as rescue therapy (Section 2.14.9). Such intake is to be recorded (see below). Contact lens wear is strictly prohibited from the time of screening throughout the study. If participant has current contact lens use at screening, contact lens use should be discontinued immediately, and a 14 day ocular surface stabilization period is needed between screening and baseline.

Concomitant medications are to be recorded in the eCRF.

The medical monitor should be contacted if there are any questions regarding concomitant or prior therapy.

2.14.9 *Rescue Therapy*

Participants meeting any of the following criteria would qualify for rescue with anti-VEGF therapy and/or PRP laser after consultation with the medical monitor:

Objective Rescue Therapy Criteria:

- Worsening DRSS level to 65 or higher as confirmed by the central reading center
- Development of ASNV
- Decrease in BCVA of ≥ 10 ETDRS letters from BL associated with presence of new fluid or an increase in fluid in the central subfield compared to baseline at any visit

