2.14.10.1 Permanent Discontinuation

In rare instances, it may be necessary for a participant to permanently discontinue (definitive discontinuation) study intervention. If study intervention is permanently discontinued, the participant may remain in the study for continued assessment of safety and efficacy outcomes.

Unscheduled visits may be performed as deemed appropriate by the investigator, in particular, in case of withdrawal due to an AE.

Participants *must* be withdrawn from the *study intervention* for any of the following reasons:

- If rescue therapy has been initiated
- Safety concerns for a participant by the investigator or the sponsor
- Vision threatening complication meeting rescue criteria and/or progression to worse than mild PDR with DRSS > 61
- Pregnancy (see [Section 2.17.4](#) for details)

Necessity to withdraw the participant from the study will be assessed case-by-case by the investigator in consultation with the medical monitor.

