2.15.1 Schedule of Activities

Table 1 OTT166 201 Phase 2 DR Study: Schedule of Activities (Through Week 24 – Primary Endpoint)

Study Procedure	Screening Visit 1	Baseline (BL) Visit 2	Visit 3	Visit 4	Visit 5	Visit 6	Visit 7	Visit 8 ^a
Week	--	0	4	8	12	16	20	24
Day (visit window)	-21 to -1	1	29 ± 7 days	57 ± 7 days	85 ± 7 days	113 ± 7 days	141 ± 7 days	169 ± 7 days
Screening/Baseline (BL):								
Informed consent	X							
Inclusion/exclusion	X	X						
Medical and ophthalmic history	X							
Demographics	X							
Randomization		X						
Interval Medical Review:								
Review of concomitant medications	X	X	X	X	X	X	X	X
Continue study treatment ^b		X	X	X	X	X	X	
Ocular Assessmentsⁿ:								
Refraction and BCVA (ETDRS)	OU	OU	OU	OU	OU	OU	OU	OU
Slit lamp examination	OU	OU	OU	OU	OU	OU	OU	OU
Assessment of cornea ^c	OU	OU	OU	OU	OU	OU	OU	OU
Intraocular pressure ^d	OU	OU	OU	OU	OU	OU	OU	OU
Indirect ophthalmoscopy	OU	OU	OU	OU	OU	OU	OU	OU
4-wide or 7-field color fundus photography (mandatory) ^e	OU	OU	SE	SE	OU	SE	SE	OU
SD-OCT (widerfield if available)	OU	OU	SE	SE	OU	SE	SE	OU
OCTA (if available)	OU							OU
Wide field Fluorescein Angiography ^m	OU							OU
Gonioscopy	OU							OU

Study Procedure	Screening Visit 1	Baseline (BL) Visit 2	Visit 3	Visit 4	Visit 5	Visit 6	Visit 7	Visit 8 ^a
Week	--	0	4	8	12	16	20	24
Day (visit window)	-21 to -1	1	29 ± 7 days	57 ± 7 days	85 ± 7 days	113 ± 7 days	141 ± 7 days	169 ± 7 days
Non-Ocular Assessments:								
Physical examination ^f	X							
Vital signs ^g	X	X	X	X	X	X	X	X
Adverse events ^h	X	X	X	X	X	X	X	X
IP adherence review ^o			X	X	X	X	X	X
Laboratory Testing:ⁱ								
Hematology, blood chemistry, urinalysis, and HbA1c ^{j,l}	X							X
Pregnancy test, women of childbearing potential ^k	serum	urine	urine	urine	urine	urine	urine	urine

Abbreviations: BCVA: best corrected visual acuity; BL: baseline; ETDRS: Early Treatment Diabetic Retinopathy Study; HbA1c: glycosylated hemoglobin; OCTA: optical coherence tomography – angiography; OU: both eyes; SD-OCT: spectral-domain optical coherence tomography; SE: study eye.

- ^a Participants who are withdrawn from the study before Week 24/Visit 8 will be asked to return to the clinic to complete the end of study assessments.
- ^b Participants will continue to receive study treatment based on exam findings, AE review, and verification that rescue criteria are not met.

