- Time to development of PDR worse than mild (DRSS 65 and above) or CI-DME
- Proportion of participants with change in DRSS steps at Week 24 compared to baseline
 - Change in DRSS steps is defined as DR worsening or improving by 1, 2, or ≥ 3 steps
- Proportion of participants with mild PDR (DRSS score 61B) at baseline who regress to NPDR (DRSS score ≤ 53) by Week 24
- Mean and median change in BCVA (ETDRS letters) from baseline to Week 24
- Lines gained/lost in BCVA ($\pm 5, 10, \text{ and } 15$ ETDRS letters) at Week 24
- Mean and median change in AUC for change in BCVA from baseline to Week 24
- Mean and median change in CST from baseline to Week 24
- AUC for change in CST from baseline to 24 weeks
- Proportion of participants who met the objective rescue criteria as defined in [Section 2.14.9](#).
- Time to meet objective rescue therapy criteria as defined in [Section 2.14.9](#).
- Time to administration of rescue therapy.

Exploratory outcomes measures will include:

- Change in Macular Volume (MV) from baseline to Week 24 for 1, 3, and 6 mm regions
 - MV will be defined as the sum of the 9 subfield measurements as provided by the imaging center
- Change in area of retinal non-perfusion from baseline to Week 24 seen on widefield fluorescein angiography (FA)
- Proportion of participants with intact foveal avascular zone (FAZ) seen on widefield FA at Week 24
- Optical coherence tomography angiography (OCTA) endpoints within the 6 mm area:
 - Change from baseline to Week 24 in FAZ area
 - Change from baseline to Week 24 in non-perfusion area
 - Change from baseline to Week 24 in vessel caliber
 - Change from baseline in ischemic Index at Week 24 defined as total area of non-perfusion divided by total area of retina visualized (28.3 mm^2)
 - Proportion of participants with new neovascularization at Week 24

- Proportion of participants with new IRMA at Week 24
- Change in vessel density from baseline to Week 24 in the superficial and deep layers

2.20.3 *Analysis Sets*

For purposes of analysis, the following analysis sets are defined:

Table 2 Analysis Sets

Analysis Set	Description
Enrolled Set (ES)	All participants who signed informed consent.
Intent-to-Treat (ITT) Analysis Set	All randomized participants who received at least one dose of study drug. Participants will be included into the analysis as randomized. This corresponds to what is referred to in ICH E9 as the Full Analysis Set.

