**3.2.2 Primary Efficacy Endpoint and Estimand**

The primary efficacy outcome measure of the study will be the proportion of participants who have improved by  $\geq 2$  steps from baseline at Week 24 as determined by central reading center assessment using the DRSS. The primary clinical question of interest is to determine the effectiveness of different doses of OCT166 versus vehicle control on  $\geq 2$  steps improvement from BL in DRSS score at Week 24 without requiring rescue treatment if the study drug is not discontinued prior to Week 24. This will support the dose selection for subsequent pivotal studies of OTT166. The estimand for the primary efficacy analysis is defined as follows:

|   | Primary Estimand  |
|---|--|
| Treatment conditions of interest | OTT166 5 mg/day, OTT166 10 mg/day and matching vehicle control   |
| Participant Population           | DR participants with Type 1 or Type 2 diabetes under adequate control (HbA1c $\leq 12.0\%$ ) who show typical fundus alterations and have been diagnosed with moderately severe to severe NPDR or mild PDR as defined by the DRSS Steps 47, 53, and 61B, with BCVA $\geq 69$ ETDRS letters, CST of $\leq 325 \mu\text{m}$ , and a normal foveal contour. |
| Endpoint                         | $\geq 2$ steps improvement from BL in DRSS score at Week 24  |
| Population level summary         | Difference in proportion of participants achieving $\geq 2$ steps improvement from BL in DRSS score at Week 24 between each OTT166 treatment group and the combined vehicle control group.   |

|   | Primary Estimand  |
|---|--|
| Intercurrent events (ICEs) and strategies to handle ICEs | 
a) Rescue treatment in the study eye due to worsening DRSS level to 65 or higher prior to assessment of DRSS at Week 24
Composite strategy (non-response)
 
b) Death prior to DRSS assessment at Week 24
Hypothetical strategy
 
c) Use of rescue treatment in the study eye for any other reason prior to DRSS assessment at Week 24
Composite strategy (non-response)
 
d) Premature discontinuation of study drug for any reason prior to DRSS assessment at Week 24
Hypothetical strategy
 
e) Study drug compliance <75% through Week 24
Treatment policy strategy
 
f) Study drug compliance between 75% to <90% through Week 24
Treatment policy strategy
 |

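### The primary imputation model omits the Week 4–20 DRSS grades, so unrescued eyes that stop drug or miss Week 24 are imputed without their own course

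*SAP*

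**What the plan says.** SAP 4.10.1.2 gives the primary imputation model in one sentence: "MAR imputation will be generated based on a regression model for DRSS levels with covariates for randomized treatment group and the randomization stratification variable". The stratification variable is the screening DRSS level (47, 53 or 61B; SAP 4.10.1.1). Response is then derived from the imputed level, with 100 imputations. The protocol calls for multiple imputation under MAR (2.21.2.1) but names no model.

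Which eyes reach this model follows from the estimand in SAP 3.2.2. Study-eye rescue, for whatever reason, counts as non-response and bypasses it; the first such event is "Rescue treatment in the study eye due to worsening DRSS level to 65 or higher prior to assessment of DRSS at Week 24". Death and "Premature discontinuation of study drug for any reason prior to DRSS assessment at Week 24" follow the hypothetical strategy, so any later Week 24 value is discarded and imputed. Week 24 grades missing without an intercurrent event use the same model.

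The grades left out are already collected. The Protocol Synopsis lists "7-field or 4-wide field color fundus photography at every visit", the Schedule of Activities includes the study eye each time, and Protocol 2.16.2 sends all photographs to the central reading center for DRSS grading.

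**The concern.** Under this model, missingness is treated as unrelated to outcome once arm and stratum are known. That is weak for a participant whose eye was graded up to five times between Weeks 4 and 20 and who then stopped. The hypothetical strategy asks what would have happened had drug continued. The eye's own course before the event is the best available evidence on that, and the model does not use it.

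The documents contain one route where this clearly matters. Protocol 2.14.10.1 requires withdrawal from study drug for "Vision threatening complication meeting rescue criteria and/or progression to worse than mild PDR with DRSS > 61". Footnote b of the Schedule of Activities agrees: "Participants will continue to receive study treatment based on exam findings, AE review, and verification that rescue criteria are not met". Rescue is a separate step: under Protocol 2.14.9 such participants "would qualify for rescue with anti-VEGF therapy and/or PRP laser after consultation with the medical monitor". Protocol 2.20.2 lists "Time to administration of rescue therapy" apart from the time to meeting the objective criteria. The first intercurrent event is keyed to rescue, not to progression. An eye that reaches level 65 and stops without rescue is therefore a discontinuation, and it is imputed as a typical eye of its arm and stratum. At the design rate that means roughly a 26% chance of being counted a responder on active drug, despite recorded worsening.

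Replacing values observed after discontinuation follows from the hypothetical strategy and is not the fault. The fault is the choice of predictors. SAP 4.10.1.2 carries the same approach over to the secondary endpoints that are proportions.

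**Working it through.** **Inputs from the documents.** Vehicle rate 0.06 and difference 0.20, so active 0.26; one-sided alpha 0.05; at least 90% power; 66 completers per group from 70, with about 5% attrition (SAP 4.13).

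**The plan's own figure.** Uncorrected n = [1.645·√(2·0.16·0.84) + 1.282·√(0.26·0.74 + 0.06·0.94)]² / 0.20² = 55.65. With continuity correction, n = (55.65/4)·[1 + √(1 + 4/(55.65·0.20))]² = 65.3, so 66. Power at 66 is 0.903, and 66/0.95 = 69.5, so 70. The sample size reproduces and is not in question.

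**Yardstick.** SE of the difference = √(0.26·0.74/66 + 0.06·0.94/66) = 6.14 points.

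**Step 1: the documented route, closed form.** Let k of 70 eyes in an arm progress, stop unrescued and be true non-responders. Observed eyes then respond at p·70/(70−k), so arm bias = p·k/(70−k).
- k = 4 in each arm: active 0.26·4/66 = 1.58 points, vehicle 0.06·4/66 = 0.36, difference +1.21.
- k = 1, 2, 3 in each arm: +0.29, +0.59, +0.90.
- 2 active and 4 vehicle: 0.26·2/68 − 0.06·4/66 = 0.76 − 0.36 = +0.40.
- Assuming 3% of active and 6% of vehicle eyes reach level 65 and none is rescued: 0.26·0.03/0.97 − 0.06·0.06/0.94 = 0.80 − 0.38 = +0.42. Simulation gives +0.34 to +0.42, and +0.17 to +0.21 if half are unrescued.

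**Step 2: stopping that depends on interim course (assumed).** Simulation with 1,000,000 per arm. Stratum weights were 0.35/0.50/0.15. Step changes (−2 or better, −1, 0, +1, +2) were 6/14/60/14/6% on vehicle and 26/20/44/7/3% on active. Interim-to-Week 24 correlation was 0.5 to 0.8, and stopping was logistic in the interim step with slopes 0.5 to 2. Levels 47, 53, 61 and 65 were taken as consecutive steps. Bias in the difference, in points:

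| Imputed, active/vehicle | Non-improvers stop | Improvers stop |
|---|---|---|
| 5%/5% | +0.2 to +0.9 | −0.2 to −0.6 |
| 10%/10% | +0.5 to +1.8 | −0.5 to −1.5 |
| 10%/5% | +0.6 to +2.1 | −0.6 to −2.5 |
| 5%/10% | +0.1 to +0.6 | −0.1 to +0.4 |

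Adding the exact interim step brings the bias within 0.06 point. A separate single-stratum simulation with a normal latent scale (correlation 0.6 to 0.8, poorer eyes missing more often) gives +0.5 to +1.0 at 5%/5% and +1.6 to +2.9 at 15%/15%, with about zero bias once the Week 20 value is added. With 6% true response in both arms and 10% against 5% stopping, the spurious difference is +0.1 to +0.3 or −0.1 to −0.9, so a false positive is not the worry.

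**Step 3: the remedy at trial size.** 1,200 simulated trials of three groups of 70; predictive mean matching on the Week 24 step (5 donors, 20 imputations); MH risk difference compared with the complete-data value. Monte Carlo error is at most 0.08 point. The first four rows use correlation 0.8.

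| Scenario | Bias, present model | Bias, interim step added | Error, present | Error, added |
|---|---|---|---|---|
| 5%, non-improvers stop | +0.60 | −0.11 | 1.27 | 0.81 |
| 10%, non-improvers stop | +1.21 | −0.22 | 1.99 | 1.13 |
| 10%, improvers stop | −1.48 | −0.46 | 3.09 | 2.28 |
| All level-65 eyes unrescued | +0.25 | −0.02 | 0.78 | 0.14 |
| 10% missing completely at random | −0.17 | −0.37 | 2.07 | 1.69 |

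If the interim grade has reliability 0.6 (10%, non-improvers stop), bias goes from +1.12 to +0.21. At correlation 0.5 it goes from +0.66 to −0.36 with an exact grade, and from +0.69 to +0.02 at reliability 0.6.

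**The case against.** The strongest reply is about size. At the only rate the documents state, the bias is at most about 0.15 SE (0.9/6.14) and its direction is unknown, because no passage links stopping to smaller DRSS changes. This is a Phase 2 dose-selection study. If imputation and sampling errors are independent, total error at 5% imputed falls only from √(6.14² + 1.27²) = 6.27 to √(6.14² + 0.81²) = 6.19, about 1%; at 10% the gain is about 3%. All of that stands, and it is why the point is an improvement and not a threat to validity.

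The progression route is also narrow. Level 65 is itself a rescue criterion, so many such eyes may be rescued and counted as non-responders. The k = 3 and k = 4 cases need 4.3% and 5.7% of active eyes to progress unrescued, more than the 3% assumed elsewhere. This stands too; +0.42 is the better upper figure for that route.

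A further objection is that every eye above level 61 must leave drug, so the richer model has no on-drug donors there and must extrapolate. Repeat runs with no on-drug donor at level 65 still cut the error from 0.77 to 0.11. Under missingness completely at random, repeat runs gave 2.08 to 1.75, although bias grows slightly (table above).

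Grades also differ in their basis. Screening used angiography as well as photographs (SAP 4.2), and angiography is not scheduled at Weeks 4–20 but is required once worse-than-mild PDR is diagnosed (Schedule of Activities, footnote e). That limits the gain but does not remove it.

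Finally, the LOCF and time-to-improvement analyses in SAP 4.10.2 do use interim grades. Neither keeps the primary estimand while changing only the imputation model. The SAP amendment log mentions using data up to the event, but it describes superseded text and settles nothing about the current section.

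**Conclusion.** The concern holds. The primary model leaves out centrally graded interim DRSS that is already collected, and an eye with recorded progression that stops unrescued can be imputed as a responder. The likely bias is under 1 point at 5% imputed and at most about 0.3 SE (1.8 points) at 10% in both arms. It can reach +2.1 or −2.5 points if stopping is twice as common on active drug. It runs in either direction, depending on who stops.

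Only the 6% and 26% rates, the group sizes and the roughly 5% attrition come from the documents. Stopping rates, step-change distributions, stratum weights, step coding, correlations, reliabilities and k are assumptions. Attrition of 5% does not cap the imputed share, because participants may stop drug and stay in the study (Protocol 2.14.10.1). The change should be made before unmasking; confidence in the size of the benefit is medium.

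**What to change.** In SAP 4.10.1.2, impute the Week 24 DRSS step on the 12-step scale from arm, stratum and the last one or two post-baseline steps observed before any intercurrent event handled by the hypothetical strategy. Include the grade at the visit that led to stopping. Name a method that copes with sparse data, such as predictive mean matching or an ordinal model with collapsed categories, and derive response from the imputed step. Participants with no post-baseline grade before the event are imputed from arm and stratum. Keep the arm-and-stratum model as a sensitivity analysis.

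The cost is SAP wording and programming; no new data are needed. The limits should be stated. Cells are small: about 70 per group, with 61B at most about 14 (20% of 70). Photograph-only grades may recover only part of the bias. Predictive mean matching pooled over arms pulls the difference down slightly.
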